2. BACKGROUND INFORMATION AND SCIENTIFIC RATIONALE

1. Background Information

With the rise of the COVID-19 global pandemic, society has fundamentally changed. The delivery of healthcare services has shifted dramatically to telehealth from in-person care, and there has been a dramatic jump in the incidence of mental distress in the U.S. (1)

Major Depressive Disorder (MDD) is the leading cause of disability worldwide. Depression and anxiety disorders are among the most prevalent of all mental disorders, with an estimated annual prevalence of 9.7% and 18.1% respectively (2).

Kintsugi, a digital health technology company based in Berkeley and founded in 2019, has developed a consumer application called Kintsugi that is available on the Apple App Store. This app allows users to journal by speaking, and interact with community members who share similar challenges to promote mental wellbeing. Based upon their preliminary work and user engagement, Kintsugi team has been awarded several National Science Foundation SBIR grants to develop new Artificial Intelligence (AI) technologies in healthcare. Most recently, the team has developed an AI-based algorithm that is able to detect depression and anxiety from short clips of free-form speech. Kintsugi Voice Biomarker API (KiVA™) is the product based on this algorithm.

AI has great potential to augment healthcare in the form of clinical decision support tools for clinicians or as a standalone autonomous solution.

Voice biomarker technologies provide a unique way to scale access to mental healthcare by assisting clinicians with triage especially in high-volume environments where administrative burdens are high. Researchers have attempted to find objective methods to increase the accuracy of depression and generalized anxiety disorder diagnoses, and voice-based biomarkers are attractive because of their non-invasive nature and ability to provide passive monitoring.

2. Scientific Rationale

Voice biomarkers detect a variety of health conditions, emotions, and diseases and provide non-invasive ways to collect patient feedback. Transforming voice intonations into voice biomarkers would allow us to predict the existence of disease, monitor progression or deterioration of disease or chronic condition, predict hospitalization and mortality, focus on patients in need, and as a result, optimize health care outcomes and cost.

It has been known for the last 100 years that depression and anxiety both likely affect vocal acoustic properties. In 1921, Emil Kraepelin, characterized depressed patient's voices as having a lower pitch, lower volume, lower rate of speech, more monotony of prosody as well as more hesitations, stuttering, and whispering (3). Various groups of researchers, such as Zhang et al (2020), Espinola et al. (2020), Wang et al (2019), Smiljanic et al. (2019) have tried to

characterize the most salient vocal acoustic (paralinguistic) features in depression, to develop a possible biomarker for the condition. (4-11)

Mechanistically, it is possible that the neural circuitry involved in the pathophysiology of mood and anxiety disorders impinge upon the neural circuit involved in speech production, affecting qualities that include rate, prosody, speech latency and other paralinguistic features. Thus, acoustic features of speech may be one of the more readily accessible biomarkers for these conditions.

Given this understanding, we sought to develop a passive vocal biomarker instrument for depression and anxiety screening that could markedly expand access as well as standardize the quality of screening in primary care settings.

Numerous research groups have studied human voice and its acoustic features for its suggested correlation with psychiatric disorders. (12-17) General understanding in the field of vocal analysis about vocal features that construct perceptually relevant amplitude and frequency representations led us to use mel-frequency cepstral coefficients (MFCCs) for our experiments. Mel-frequency cepstral coefficients (MFCCs) are coefficients that collectively make up a Mel-frequency cepstral (MFC). MFCCs in turn are a representation of the short-term power spectrum of a sound. (18) Features that we extract represent phonemes (distinct units of sound) as the shape of the vocal tract. Sounds generated by humans are filtered by the shape of the vocal tract that includes tongue, teeth, lips, throat, et cetera and determines the sounds produced. In addition to MFCCs, other characteristics such as fundamental frequency, frequency variability, shimmer, jitter and pause length are also considered in our modeling efforts.

2.3 Potential Risks and Benefits

2.3.1 Potential Risks

Potential risks associated with this study include:

- Breach of confidentiality of personal information
- Participation may bring up emotionally charged content which could temporarily impact participants' mood

The probability of breach of confidentiality will be minimized by storing all data in a secure, password protected Google Cloud Platform storage. Researchers will also be using Named Entity Recognition (NER) and number detection scripts to strip out any person names, organizations, locations, medical codes, quantities, medical record numbers, monetary values, and percentages. The PI and the Research Coordinators will be the only people with access to the Google Cloud Platform bucket. After the study concludes, participants' First and Last name, email and phone number will be deleted.

The probability of discomfort related to probing for emotionally charged content will be minimized by the Research Coordinator reminding the subjects to answer the questions at their own comfort level. All the participants will be emailed a list of resources before

the study begins. List of resources will include phone numbers of various services that can be contacted immediately if a participant experiences distress or discomfort.

2.3.2 Known Potential Benefits

While there may be no direct benefit from participation in the study, possible indirect benefits of voice journaling include:

- Reduction in anxiety
- Reduction in stress

3. OBJECTIVES

The objective of this study is to collect data to improve the sensitivity and specificity of KiVATM's predictions on audio files. A web-based audio recording tool will be used to record voice sample and ask participants the PHQ-9 and GAD-7 questions. Participants will then be assessed by mental health professionals with the Hamilton Depression Rating Scale (HAM-D) (19, 20) and Hamilton Anxiety Rating Scale (HAM-A) (21) scores.

Ultimately, the results of this study will allow us to create a technology that can scale access to mental healthcare by increasing the rates of depression and anxiety screening and routing patients to the appropriate level of care.

4. STUDY DESIGN

This is a prospective, fully remote observational e-clinical study to improve the sensitivity and specificity of KiVA™ predictions against clinician-rendered HAM-D and HAM-A scores.

The duration of the study enrollment is anticipated to continue until ~1,000 participants are enrolled. We will extend the enrollment period until the necessary number of participants is enrolled.

5. STUDY POPULATION

5.1 Selection of the Study Population

This study will enroll ~1,000 men and women over the age of 18 via social media.

5.2 Inclusion Criteria

- Adult males and or females over the age of 18 at the time of informed consent. Adults with a known history of depression and/or anxiety and adults without a known history of depression and/or anxiety will be included in this study.
- Access to a laptop, smartphone or tablet with a functioning microphone
- Stated willingness to comply with all study procedures and availability for the duration of the study
- Fluency in English

5.3 Exclusion Criteria

- Visual impairment that would make it difficult for the participant to see the web-based survey
- Motor impairment that would make it difficult for the participant to use the web-based survey

6. RECRUITMENT AND RETENTION

The study research coordinators will recruit participants from social media, such as Reddit and Facebook.

Participants will receive a link to our web-based audio survey from social media advertisement or message to complete the study steps.

Potential participants will be offered an Amazon Gift card, PayPal or Visa card of \$ 5 or \$10 for participating in the first part of the study. Potential participants who qualify for the second part of the study will be offered an Amazon Gift card, PayPal or Visa card of \$50. The gift card will be distributed via email after the participant completes the study. Partial completion of the study requirements will not be paid.

Additionally, participants will be able to download the Kintsugi voice journaling app at no cost once they enroll in the study. The usual cost for the app is \$19.99.

For the second part of the study, participants will be selected from the pool of participants that completed the first part. The Research Coordinator will email those participants who scored greater than 20 on their PHQ-9 questionnaire with an offer to participate in the second part of the study.

7. STUDY PROCEDURES/EVALUATIONS

7.1 PART I

Participants will follow the link from the social media advertisement or message in order to participate in the study.

They will review the Informed Consent Form (ICF). The ICF provides a detailed explanation of the risks and benefits of the study. By accepting the ICF, the participant agrees to enroll in the study.

We have a different informed consent form and different reward rate depending on the social media platform that the participant comes from. The reason for this is because participants from social media such as Reddit have a higher prevalence of depression than participants from social media such as Facebook.

The participant will be asked to take the online survey. He or she will answer the following questions aloud:

How are you feeling today? Please speak for 1 minute about your day, if there was anything special about it and overall, how you felt.

After the recorded section, participants will complete two self-assessments: PHQ-9 and GAD-7. The Patient Health Questionnaire and Generalized Anxiety Disorder tests have 16 questions in total. These assessments will immediately follow the recorded section.

The Research Coordinator will email a \$5 Amazon Gift card, PayPal or Visa card to participants from social media such as Facebook and a \$10 Amazon Gift card, PayPal or Visa card to the participants from social media such as Reddit.

Completion of this first part will take about 10-minutes.

We collect the participant email addresses because the Research Coordinator provides the gift cards via email. The information is stored on a password protected location only accessible to the PI and the research coordinators. When the study is over, the Personal Health Information (the email addresses) will be deleted.

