11. DATA HANDLING AND RECORD KEEPING

Research records will be kept in compliance with ICH E6, Section 4.9 and regulatory requirements for the protection of confidentiality of participants. The Research Study staff will permit authorized representatives of regulatory agencies to examine (and when required by applicable law, to copy) research records for the purposes of quality assurance reviews, audits, and evaluation of the study safety, progress and data validity.

Audio recordings will be saved on a password-protected Google Cloud Platform bucket that is only accessible to authorized personnel.

The audio recordings and HAM-D/HAM-A score data will be maintained for at least three years following the completion of the study. Participant confidentiality will be maintained by deleting the participants' Personal Identifiable Information (Email, Phone number, First and Last Name) and using codes once the study concludes.

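### No procedure shown in the protocol records age or sex, although the voice model draws on features tied to the speaker's vocal tract and pitch

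*Protocol*

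**What the plan says.** **Population.** Section 5.1 of the protocol states "This study will enroll ~1,000 men and women over the age of 18 via social media". Section 5.2 sets only a lower age limit: "Adult males and or females over the age of 18 at the time of informed consent". The exclusions in section 5.3 concern visual impairment and "Motor impairment that would make it difficult for the participant to use the web-based survey", so nothing narrows the sample by age or sex.

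**Features.** The scientific rationale in section 2 says that MFCCs are used and explains them through anatomy: "Sounds generated by humans are filtered by the shape of the vocal tract". It adds that "other characteristics such as fundamental frequency, frequency variability, shimmer, jitter and pause length are also considered in our modeling efforts".

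**Data collected.** In Part I (section 7.1) the participant records one spoken answer, and then "After the recorded section, participants will complete two self-assessments: PHQ-9 and GAD-7"; email addresses are also collected. Part II (section 7.2) has three recordings and the same two questionnaires. Part III (section 7.3) adds HAM-D, HAM-A, a concomitant medication log and clinical notes.

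**Identifiers.** Section 11 says that confidentiality is kept by deleting "Personal Identifiable Information (Email, Phone number, First and Last Name) and using codes once the study concludes". Sections 2.3.1 and 10.2 name the same identifiers. Neither sex nor date of birth is among them.

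**The concern.** The aim in section 3 is better sensitivity and specificity for depression and anxiety from voice. Vocal-tract shape and fundamental frequency are properties of the speaker as well as possible carriers of mood. I take it as a premise, which the protocol does not state, that they differ between men and women and change with age. If high and low scorers in this social-media sample also differ in sex or age mix, part of what the model learns may be the type of speaker.

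The protocol accepts this reasoning for another factor. Section 7.3 collects a medication log so that the effect of medication on the voice can be told apart from that of depression and anxiety. Nothing comparable is listed for age or sex.

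Three things are at stake: attributing a gain in accuracy to mood, checking that accuracy holds in both sexes and across ages, and comparing the voice model with one that knows only age and sex. What participants are asked is settled in the protocol. A later analysis plan can choose how to adjust, but it cannot supply self-reported values that were never requested.

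**Working it through.** **Step 1: search for the variables.** The protocol states no figure on this point, so there is none to reproduce. The check is whether age or sex appears as a recorded item.

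| Place in the protocol | Items named | Age or sex recorded? |
|---|---|---|
| 5.2 | age threshold at consent | threshold only; no step says how it is checked or stored |
| 7.1 (Part I) | one recording, PHQ-9, GAD-7, email | no |
| 7.2 (Part II) | three recordings, PHQ-9, GAD-7 | no |
| 7.3 (Part III) | HAM-D, HAM-A, medication log, clinical notes | not listed; content of the notes unspecified |
| 9.1.1 | HAM-D, HAM-A | no |
| 2.3.1, 10.2, 11 | email, phone, first and last name | no |
| 10.2 (kept indefinitely) | audio, HAM-D and HAM-A scores | no |

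**Step 2: look for substitutes.**
- Clinical notes might mention age or sex. They exist only for people who scored above 20 on the PHQ-9 (sections 6 and 7.2) and completed the interview, so they do not cover the rest of Part I.
- First names suggest sex at best, and they are deleted when the study ends.
- The audio is kept, so sex could be inferred from it. That inference uses the same signal that the model uses, so it is not an independent record.
- Age in years has no comparable substitute in the listed data.

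**Step 3: illustrate the possible size for sex.** Let p1 be the share of women among cases and p0 the share among non-cases. Take a marker that reads sex perfectly and calls every woman a case.

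- Sensitivity = p1 and specificity = 1 − p0.
- AUC of a binary marker = (sensitivity + specificity)/2 = 0.5 + (p1 − p0)/2.

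The protocol gives no sex mix, so p1 − p0 is assumed:

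| Assumed p1 − p0 | AUC of a sex-only marker |
|---|---|
| 0.05 | 0.5 + 0.025 = 0.525 |
| 0.10 | 0.5 + 0.05 = 0.55 |
| 0.15 | 0.5 + 0.075 = 0.575 |
| 0.20 | 0.5 + 0.10 = 0.60 |
| 0.30 | 0.5 + 0.15 = 0.65 |

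With no imbalance (p1 = p0) the AUC is 0.5 and sex adds nothing. The table describes a marker that knows only sex. It does not say by how much KiVA's own AUC would rise, because that depends on what the model already draws from mood. No figure is offered for age.

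**The case against.** The strongest reply is that section 7 is not a complete inventory. Names and phone numbers are held and later deleted according to sections 2.3.1, 10.2 and 11, yet no step in sections 7.1 to 7.3 collects them. Eligibility depends on age, so age must be ascertained somehow, and section 10.2 keeps an enrolment log whose contents are not stated. The survey screens and consent forms are not shown. This stands as a limit on wording. A reader might infer that age and sex are definitely not collected, but the document supports only that no procedure shown lists them. The gap differs from that for names and phone numbers, however: those appear elsewhere in the protocol, whereas age and sex appear nowhere as recorded items.

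A second reply is that a reader might conclude the signals can never be separated and that no analysis could repair this. That goes too far. If voice reveals sex well, as the illustration assumes, sex can be partly recovered from the retained audio, and the notes may help for interviewed participants. What remains is that such recovery is inferred or partial, and it is weakest for age.

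Third, the imbalance is assumed. HAM-D and HAM-A, the primary outcomes, are obtained only in people selected for a PHQ-9 above 20, and the sex mix of cases and non-cases within that group is unknown. This stands, and it is why the AUC range is an illustration only.

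Fourth, sensitivity and specificity against the Hamilton scales can be calculated without age or sex. That is correct: the loss is in attribution and in checking subgroups, not in the ability to compute the measures.

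Finally, rules for balancing or weighting the training data are ordinary analysis-plan content, and their absence from section 9.2 is not a fault. Collecting the variables is a matter for the protocol.

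**Conclusion.** The point holds in a limited form. No procedure shown in the protocol lists age or sex. The study enrols adults of both sexes with no upper age limit, and the features include MFCCs tied to vocal-tract shape, with fundamental frequency considered rather than stated as used. Followed as written, the data set lacks self-reported age and sex. Speaker and mood signals could then not be reliably separated, and performance by sex and age group could not be checked.

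The size in this trial cannot be determined from the document. The AUC range of 0.525 to 0.65 rests on an assumed imbalance of 5 to 30 percentage points and on perfect recognition of sex from voice. A reader might take it as the amount by which KiVA's accuracy would be overstated; the document does not support that. This is a cheap improvement worth making, not a defect that invalidates the study.

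**What to change.** Add two items to the Part I web survey in section 7.1: self-reported age in years and self-reported sex. State in sections 10.2 and 11 that both are kept under the study code after names, email and phone numbers are deleted. If they are already collected through a screen or form not shown, say so in section 7.1 and confirm that they are retained.

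This would allow performance to be reported by sex and age group and compared with a model that uses only age and sex. The choice of balancing or weighting can be left to the analysis plan.

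The cost is a few seconds per participant in a part that takes about 10 minutes, a line in the ICF, two more retained fields, and the IRB approval that section 10.1 requires for any amendment. It should be done before identifiers are deleted, while anyone already enrolled can still be reached by email.

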7.2 PART II

The Researcher will review PHQ-9 scores of all the participants and select the subset that scored greater than 20. She or he will email the subset of participants about the opportunity to participate in the next part of the study.

After receiving an email where the participant expresses interest in the next part of the study, the Research Coordinator will send an email to the participants containing:

1. Instructions on how to set up an appointment with a mental health professional with appropriate experience
2. List of resources to contact if the participant were to experience distress

After participants set up an appointment through a scheduling program, they'll receive a confirmation email with a link to a web-conferencing tool. The participant communication is included as "Participant Communication for Part II of Study Procedure".

Completion of this first part will take about 15-minutes.

The participant will review the Informed Consent Form (ICF). The ICF provides a detailed explanation of the risks and benefits of the study. By accepting the ICF, the participant agrees to enroll in the next part of the study.

The participant will be asked to take the online survey. He or she will answer the following questions aloud:

1. *How are you feeling today? Please speak for 1 minute about your day, if there was anything special about it and overall, how you felt.*
2. *What is your biggest source of stress and why?*

3. What or who are you grateful for today?

After three recorded sections participants will complete two self-assessments: PHQ-9 and GAD-7. The Patient Health Questionnaire and Generalized Anxiety Disorder tests have 16 questions in total. These assessments will immediately follow the recorded section.

Enrollment will be on a rolling basis and last however long it takes to recruit the required number of participants.

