7.3 III

Immediately after completing Part II, participants will receive a clinical assessment from a mental health professional (MHP). A web-conferencing tool link to their appointment will be provided in the confirmation email. Participants will be reminded that this is only a clinical assessment and will not involve treatment of any kind.

MHPs will fill out the Hamilton Depression Rating Scale (HAM-D) and Hamilton Anxiety Scale (HAM-A), keep a copy of the spreadsheet for their records and for subsequent data monitoring activities. Along with the spreadsheet, MHPs will send the concomitant medication log and clinical notes to the research coordinators. Some medications affect voice biomarkers and we want to be able to separate the effect of depression and anxiety vs medication from the voice biomarkers. The information is stored on a password protected location only accessible to the PI and the research coordinators. When the study is over, the Personal Health Information (the email addresses) will be deleted and coding will be used to match the records going forward.

Completion of this part will take about 30-minutes. The participant does not get a copy of their assessment and will not be able to see their assessment results.

Once participants have been evaluated by the MHP using the HAM-D and HAM-A the Research Coordinator will email the \$50 Amazon Gift card, PayPal or Visa cards.

Kintsugi staff and any data analysts will be blinded to the HAM-D and HAM-A scores.

The MHPs are either licensed mental health professionals or PhD students who have relevant experience assessing mental health patients as part of their course work. MHPs are remunerated at their market rate for conducting the clinical assessment. The MHPs do not provide any treatment to the participants. The MHPs provide a list of additional resources for the participant if they experience distress or discomfort (see page 2 of Participant Communication for Part II of Study Procedure attachment). MHPs are instructed not to establish any clinical relationship with the participant.

The MHPs are instructed to set all of their appointments with participants to private so that no one else can see these appointments. The MHPs have access to email addresses of the participants they assess because it's necessary to set up the video appointments. .

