9. STATISTICAL CONSIDERATIONS

9.1 Study Outcome Measures

9.1.1 Primary Outcomes

- Hamilton Depression Rating Scale.
 - Participants will be interviewed by MHPs using the clinically validated HAM-D tool.
- Hamilton Anxiety Rating Scale.
 - Participants will be interviewed by MHPs using the clinically validated HAM-A tool.

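### Only people with a Part I PHQ-9 above 20 are offered the HAM-D/HAM-A interview, so the specificity aim has no reference scores at or below that cut

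*Protocol*

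**What the plan says.** **Aim and reference standard.** Protocol Section 3 begins "The objective of this study is to collect data to improve the sensitivity and specificity of" KiVA's predictions. Section 4 names the comparator: "against clinician-rendered HAM-D and HAM-A scores". HAM-D and HAM-A are the only primary outcomes (Section 9.1.1: "Participants will be interviewed by MHPs using the clinically validated HAM-D tool", with a matching line for HAM-A). Section 9.2 says the data will train a machine learning model.

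**Population.** Section 5 plans about 1,000 adults and expressly admits people with and without a known history of depression or anxiety.

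**Who is interviewed.** Section 7.2: "The Researcher will review PHQ-9 scores of all the participants and select the subset that scored greater than 20". Section 6 repeats the rule: the coordinator emails those participants "who scored greater than 20 on their PHQ-9 questionnaire with an offer to participate in the second part of the study". It adds that for this part "participants will be selected from the pool of participants that completed the first part". Section 7.3 places the Hamilton interview directly after Part II. No control sample and no other route to a HAM-D or HAM-A score is described. GAD-7 is collected in Part I (Section 7.1) but plays no part in selection.

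**The concern.** Specificity is a property of people who are negative on the reference standard. The invitation rule keeps only those who have just reported severe depressive symptoms, and gives no reference score to the rest. A model trained or checked on the resulting HAM-D/HAM-A labels sees no one with a Part I PHQ-9 of 20 or less. Its few negatives are people who scored high on self-report and low at interview, which is an unusual group.

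For anxiety the mismatch has a second side. HAM-A has equal standing as a primary outcome, but access to it is decided by a depression score alone. Part I PHQ-9 and GAD-7 labels do cover the full range, but they are self-report and not the reference that Sections 4 and 9.1.1 name.

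**Working it through.** **Step 1. The empty stratum (no assumptions).** Invitation requires a Part I PHQ-9 above 20 (Sections 6 and 7.2). Part II draws only on Part I completers (Section 6). HAM-D/HAM-A are filled in only after Part II (Section 7.3). The number of Hamilton scores for Part I PHQ-9 of 20 or less is therefore 0 at any enrolment.

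**Step 2. How many HAM-D-negatives the rule yields (illustration).** The protocol gives no share above 20, no uptake, no number of interviews and no HAM-D cut-off, so every input here is assumed. Treat Part I PHQ-9 and HAM-D as bivariate normal with correlation *r* = 0.6, 0.7 or 0.8; share above the PHQ-9 cut *f* = 5, 10 or 20%; HAM-D positive *p* = 30 or 50%. That makes 18 scenarios. With a = Φ⁻¹(1−f), b = Φ⁻¹(1−p) and J = Φ₂(a, b; r):

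- negative share above the cut: q₁ = [(1−p) − J]/f
- negative share at or below the cut: q₀ = J/(1−f)

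Over the 18 scenarios q₁ runs from 0.0053 to 0.357. Of all HAM-D-negatives, 89.8% to 99.95% lie at or below the cut.

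**Step 3. Same number of interviews, two ways to allocate them.** Take 50 interviews as a scale. The rule gives 50·q₁ negatives; an even split gives 25·q₁ + 25·q₀.

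| Scenario | q₁ | q₀ | Rule | 25/25 split | Split, effective after weighting |
|---|---|---|---|---|---|
| r 0.8, f 10%, p 30% | 0.095 | 0.767 | 4.8 | 21.6 | 19.7 |
| r 0.8, f 20%, p 30% | 0.200 | 0.825 | 10.0 | 25.6 | 22.9 |
| Range over all 18 | 0.005-0.357 | 0.523-0.825 | 0.3-17.9 | 13.3-28.6 | 13.2-23.7 |

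The last column weights the split back to the enrolled mix, with weights f/0.5 above and (1−f)/0.5 below, and uses Kish's (Σw)²/Σw². For the first row: (2.4×0.2 + 19.2×1.8)² / (2.4×0.04 + 19.2×3.24) ≈ 19.7. Design effects are 1.01-1.26.

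**Step 4. Precision at about 80% observed specificity** (Clopper-Pearson 95%, unweighted). First row: 4/5 gives 28-99%, against 58-95% for 17/21. Second row: 8/10 gives 44-97%, against 59-93% for 20/25.

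**Step 5. Scaled to the planned enrolment.** With 1,000 Part I completers and assumed uptake of 30% or 70%, equal on both sides of the cut, interviews number 1,000·f·uptake = 15-140. The rule then yields 0.1-50 negatives and an even split of the same total 4-80. The rule gives fewer than 5 negatives in 18 of 36 scenarios.

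**Step 6. Are those negatives representative?** A simulation assumed 40% HAM-D positive, a PHQ-9/severity correlation of 0.6-0.8, a mean PHQ-9 of 8 or 12 and a voice score correlated 0.5 with severity. Specificity was 0.73 in everyone and 0.61-0.65 among those above 20. Sensitivity was 0.60 and 0.67-0.77. So labels from the selected group misstate both quantities for the enrolled population.

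**Step 7. Anxiety.** With PHQ-9 and GAD-7 bivariate normal (r = 0.6-0.8), the same *f*, and high GAD-7 defined as the top h = 10-30%, the share of high-GAD-7 people cut off from a HAM-A is 1 − P(both high)/h. This runs from 21% (r 0.8, f 20%, h 10%) to 87% (r 0.6, f 5%, h 30%).

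**The case against.** - **The counts depend on an undefined threshold.** The protocol states no HAM-D or HAM-A cut-off, so who counts as negative is open. With a stricter cut-off giving 10% HAM-D positive (r 0.6, f 20%), the rule yields 35.1 negatives per 50 and the weighted split only 31.8 effective; at 15% they tie at 29.7. This stands: a shortage of negatives is conditional on the assumptions. Even so, every one of those negatives has a Part I PHQ-9 above 20, so coverage does not improve.
- **HAM-A-negatives are not counted.** True. Selection is on a depression scale, so they may be more common among interviewees than HAM-D-negatives. Step 7 concerns anxious people missed, not HAM-A specificity.
- **The study collects training data and promises no specificity estimate.** Also true, and Section 9.2 does not say which labels train the model. But the stated objective is data that improve specificity against the Hamilton scales, and labels confined to one extreme do not serve it.
- **Some interviewees may score lower when the PHQ-9 is repeated in Part II.** Yes, but they still come only from those above 20 in Part I.
- **Later analysis might repair it.** A separate SAP cannot change who was interviewed. Weighting fails at zero probability, and model-based prediction of the missing scores would be extrapolation that cannot be tested.
- **Enrichment may be deliberate, and the aim could be narrowed instead.** The protocol gives no such rationale. Limiting the Hamilton aim to PHQ-9 above 20 would remove the contradiction, but only by giving up specificity in the enrolled population.

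**Conclusion.** The concern holds and must be fixed before interviews are allocated. What is certain, from the text alone, is that no participant with a Part I PHQ-9 of 20 or less can receive the reference score on which both primary outcomes and the specificity aim rest. The size of the loss is illustrative. Within the assumed grid, the rule gives about 0.3-18 HAM-D-negatives per 50 interviews against 13-29 under an even split (13-24 after weighting), and 21-87% of high-GAD-7 participants are shut out of a HAM-A. A stricter HAM-D cut-off could reverse the comparison of counts but would leave the stratum empty.

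**What to change.** Replace the above-20 invitation rule in Sections 6 and 7.2 with sampling of Part I completers across the whole PHQ-9 range and across low and high GAD-7. Fix and record a known, non-zero invitation probability for each stratum, and hold the total number of interviews constant, so that results can be weighted back to the enrolled population. Amend Section 3, which reads as if every participant is assessed, to say that only the Part II/III sample receives HAM-D and HAM-A.

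The cost is a protocol amendment with IRB approval. No extra interviews are needed. The price is fewer interviews of people above the cut (25 instead of 50 in the illustration), hence less precision on severe cases.
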